7.11 Treatments

7.11.1 Identity of Investigational Medicinal Product (IMP)

Tamoxifen 1, 2.5, 5, 10, 20 mg and matching placebo are white to off white, flat, beveled edge uncoated tablets, plain on both sides.

All investigational product will be provided as a tablet for oral administration and provided in blisters.

All investigational product (tamoxifen and matching placebo) will be manufactured according to Good Manufacturing Practice (GMP).

7.11.2 Packaging, labelling and storage of IMP

The flow of the IMP:

- 1) Producer (Khandelwal Laboratories PVT Ltd)
- 2) Relabeling of CMO in Sweden (Galenica AB)
- 3) Release (Clinstorage AB)
- 4) Storage (Sjukhusapoteket Lund and Sjukhusapoteket Karolinska)
- 5) Distribution to Karma Study Center

At IMP producer (India):

The producer of the IMP produces the six doses of tamoxifen in different batches. Every dose will be produced during one series i.e. one batch. The tablets are placed in blisters (primary package) then 18 blisters will be put in a box (secondary package). All boxes of the same dose are placed in one of six tertiary packages (a tertiary package per dose). The tertiary packages are than sealed. All the (primary, secondary and tertiary) packaging is labelled with a batch

number in accordance with GMP. Labelling on blister is an adhesive label that can be removed. The six tertiary packages are sent to a CMO in Sweden (Galencia) where the primary and secondary packaging will be relabelled according to a list of randomization.

At CMO (Sweden): Blister is labeled with: Study: KarismaII

Sponsor: Karolinska Institutet

Investigator: [name]

Randomization No: [1,2, ..., 1200]

Batch No: xxx

Secondary packaging is labelled with complete information including Randomization No. QP of release in Sweden is ClinStorage AB (QP name [name]). When released the IMP will be stored at Sjukhusapoteket Lund respectively Karolinska sjukhusapoteket Solna.

The investigational product (tamoxifen and matching placebo) should be stored in the containers in which they are received from the Sponsor's supplier, preferably at room temperature, but no specific storage conditions are needed.

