Tertiary objectives: Relate levels of tamoxifen metabolites, proteins, lipids and hormones in blood and changes in breast tissue to different tamoxifen doses. Measure genetic polymorphism in germline DNA and relate it to the other tertiary objectives. Measure mammographic density and levels of side effects 6 months after tamoxifen cessation in relation to treatment arm

Tertiary endpoints: Levels of tamoxifen metabolites, proteins, lipids and hormones in blood. Breast tissue changes. Genetic polymorphism in germline DNA. Mammographic density and levels of side effects 6 months after tamoxifen cessation

Study design

Randomized, double blinded, six-armed, placebo controlled clinical trial

Number of subjects planned

1,440

Diagnosis and main eligibility criteria

Healthy women participating in mammographic screening with a a measurable mammographic density, i.e. ≥4.5 % density (volumetric) measured by Volpara.

Investigational Medical Product

Investigational product - Tamoxifen

Dosage – 20 mg, 10 mg, 5mg, 2.5 mg, 1 mg and 0 mg (placebo)

Oral administration, one tablet once daily

Duration of treatment

6 months

Duration of subjects involvement in the study

6 months for the SÖS-cohort (1400 particip), 12 months for the Lund cohort (40 paticip)

Efficacy assessments

Mammographic density after 6 months

Plasma levels of tamoxifen metabolites, proteins, lipids and hormones in blood

Genetic polymorphism measured in germline DNA

Safety assessments

Monitoring and recording of all AEs and SAEs

Statistical methods

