This is a dose determination study aiming to identify the optimal tamoxifen dose for reducing the risk of breast cancer. Instead of following a very large number of women, for many years, treated with different doses of tamoxifen and see if they develop breast cancer, we will include 1,440 healthy women participating in the mammographic screening program at two Mammography units (Unilabs mammography, Lund and Södersjukhuset Breast Centre, Stockholm) and measure their change in mammographic density. The change in mammographic density is a very good marker of therapy response. We will test if 1 mg, 2.5 mg, 5 mg and 10 mg reduce the mammographic density to the same extent as 20 mg. In summary Karisma II will be a randomized, double-blinded, six-armed placebo controlled study to identify the dose of tamoxifen with the most favourable side effect spectra and with a density reduction non-inferior to 20 mg tamoxifen.

The Karisma II study will be run in accordance with the ICH GCP guidelines, the principals of which have their origins in the Helsinki 2000 Declaration.

Karisma III

When the optimal tamoxifen dose has been identified in the Karisma II study, we intend to test this dose in women at high risk of breast cancer and study long-term effect of breast cancer incidence. In this phase we plan to include 8,000 women. A separate application will be sent for Karisma III.

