The scientific "golden standard" for measuring mammographic density is a software supported method called Cumulus. In this semi-automated approach the breast contour is outlined and a human reader decides on what part of the breast is dense. The software then calculates the dense area. The obvious weaknesses of Cumulus are that it is time consuming, labor intensive and highly reader dependent.

In clinical practice mammographic density is measured using BI-RADS. BI-RADS categorizes breast into four categories: entirely fatty, scattered areas of fibroglandular density, and extremely dense breast. The BI-RADS measurement is done by the radiologist by looking at the mammogram. BI-RADS measurements are very crude and highly reader dependent.

Volpara is a FDA approved full automatic method for volumetric density measurement that the Karma project group in collaboration with the Mammography units at Södersjukhuset and Unilabs Lund has implemented for clinical use. The Volpara method has also been validated in the Karma cohort. We will use Volpara as a tool for assessment of eligibility (measurable density), since its implemented and the measurement can be done instantly.

In the former mentioned Karma adjuvant tamoxifen therapy study we used a newly developed fully automated density measurement, the Stratus method, which mimics how Cumulus measures mammographic density but as automated tool is not reader dependent. In the Karisma II study we will use both Volpara and Stratus to analyse the mammographic changes.

The results from the Karisma I study showed that the effect of tamoxifen on mammographic density can be determined after 6 months of treatment and indicates that the effect is equal for the doses 10 mg and 20 mg. Currently there are no studies including longitudinal measurement of mammographic density on healthy women using tamoxifen. By adding a lower dose in the Karisma I study, 10 mg, we have got an indication lower doses will be sufficient for reducing density. In Karisma II we will include six arms with 200 women in each arm; 20 mg, 10 mg, 5

mg, 2.5 mg, 1 mg and a control arm with placebo. The Subjects and Investigators will be blinded.

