10.6.3 Sample size

With 168 patients in each treatment group, the lower limit of the observed one-sided 98.5% confidence limit for the difference will be expected to exceed the non-inferiority margin 16.7 percentage points with a 80% power, assuming that the expected difference in responders between two arms is 0 and the proportion responders in the 20 mg tamoxifen group is 50%. With an estimated 30% drop-out rate, 240 patients in each group need to be randomized. The computations are based on the following formula:

$$n = f(\alpha, \beta) \times [\pi_s \times (100 - \pi_s) + \pi_e \times (100 - \pi_e)] / (\pi_s - \pi_e - d)^2$$

where π_s and π_e are the true percent 'success' in the standard (20mg) and experimental treatment group respectively, and

$$f(\alpha, \beta) = [\Phi^{-1}(\alpha) + \Phi^{-1}(\beta)]^2$$

 Φ^{-1} is the cumulative distribution function of a standardised normal deviate.

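### Protocol 7.11.2 numbers the drug labels only to 1,200 and 4.1 says 200 women per arm, while the trial is sized at 1,440 (240 per arm)

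*Protocol*

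**What the plan says.** Two places in the protocol describe a trial of 1,200 women:

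- Section 7.11.2 specifies the blister label as "Randomization No: [1,2, ..., 1200". The primary and secondary packaging is to be "relabelled according to a list of randomization", so the label range is the range of that list.
- Section 4.1: "In Karisma II we will include six arms with 200 women in each arm". Six times 200 is 1,200.

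The other statements of size describe 1,440:

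- Section 4: "we will include 1,440 healthy women participating in the mammographic screening program".
- Synopsis: 1,440 planned, split by site as "6 months for the SÖS-cohort (1400 particip), 12 months for the Lund cohort (40 paticip". The site table in section 5.4 repeats about 40 and about 1,400.
- Section 10.6.3: "With 168 patients in each treatment group" as the evaluable number, then "240 patients in each group need to be randomized" after allowing for 30% drop-out.
- SAP sections 4 and 6.6: 1,440 in total and 240 per arm.

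Both sets of figures stand in current text. Neither comes from the revision history.

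**The concern.** The label range has a working role. Under sections 7.1.3 and 7.11.4 each woman is randomised at baseline, her randomisation number goes into the eCRF, and she is handed her whole six-month supply. The drug carries the randomisation number, and the contract manufacturer that relabels it also performs the randomisation (7.11.5). On this description a list ending at 1,200 holds no number for woman 1,201, although Stockholm alone is planned at about 1,400.

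Two separate sections agree on 1,200, so this is more than a stray digit. A reader preparing the list from 7.11.2 would build a different trial from a reader working from 10.6.3. If the smaller figure were followed, the primary non-inferiority comparisons would have less than their stated power.

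**Working it through.** **Inputs** (Protocol 10.6.2 and 10.6.3; SAP 6.6): one-sided 98.5% confidence limit, so alpha = 0.015 and z = 2.170; 80% power, z = 0.842; margin 16.7 points; 50% responders in both arms, true difference 0; drop-out 30%; equal allocation to six arms (Protocol 7.11.5).

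**Step 1. Reproduce the plan's figure.** The printed formula is n = f × [πs(100 − πs) + πe(100 − πe)] / (πs − πe − d)².

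- f = (2.170 + 0.842)² ≈ 9.07
- variance term = 50×50 + 50×50 = 5,000
- n = 9.07 × 5,000 / 16.7² ≈ 163 evaluable per arm, against 168 stated (within 3%)
- 168 / 0.70 = 240 randomised per arm; 240 × 6 = 1,440

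Other one-sided levels give 180 (0.01), 141 (0.025), 133 (0.03) and 111 (0.05). Only the documents' own 0.015 comes close to 168. The sample size section is consistent with itself and with the 1,440 total.

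**Step 2. Power at each size.** Power = Φ(16.7 / √(5000/n) − 2.170).

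| Randomised | Per arm | Evaluable at 30% loss | Power |
|---|---|---|---|
| 1,440 | 240 | 168 | Φ(3.061 − 2.170) = 81.4% |
| 1,200 | 200 | 140 | Φ(2.794 − 2.170) = 73.4% |

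Like for like, the difference is 81.4 − 73.4 = 8.0 points. Against the stated 80% it is 6.6 points.

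**Step 3. Sensitivity at 200 per arm.** Power depends on how many women are evaluable, holding 50% responders in both arms:

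- 25% lost: 150 evaluable, 76.5%
- 20% lost: 160 evaluable, 79.3%
- 16% lost: 168 evaluable, 81.4% (1 − 168/200 = 0.16)
- none lost: 200 evaluable, 87.9%

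**Step 4. Compare with the plan's own interim formula** (Protocol 10.6.7; SAP 6.8): total = 168 × 6 / (1 − d) = 1,008 / (1 − d).

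- d = 16%: 1,200
- d = 25%, roughly the discontinuation seen in the pilot (Protocol 4): 1,344
- d = 30%, the planning value: 1,440
- d above 30%: more than 1,440, for example 1,680 at 40%

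So 1,200 is enough by this formula only if drop-out is 16% or less, below both rates the protocol cites.

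**The case against.** The strongest reply is that 7.11.2 is a label template. The next line of the same template gives the batch number as a placeholder. The section states no number of kits or tablets, and no text says that enrolment stops at 1,200. Every passage that sets or justifies the size says 1,440, and the SAP is consistent throughout. On this view 1,200 is simply an out-of-date figure and no power is lost. This stands to the extent that the power loss cannot be stated as what the plan delivers. It does not remove the contradiction, because no passage supplies the missing numbers.

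The 73.4% also assumes that every drop-out is lost. Protocol 7.2 asks women who stop after a week or more for an exit mammogram, SAP 6.1 keeps women with one post-baseline measure in the ITT population, and SAP 6.9 carries the last observation forward. Evaluable numbers at 200 per arm could therefore lie anywhere from 140 to 200, and power from 73.4% to 87.9%. This also stands. The lower figure is the like-for-like one only because the plan's own sizing treats all drop-outs as lost.

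A reader might infer several stronger things that the documents do not support:

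- *That the drug supply is 240 kits short.* A label range is not a manufactured quantity, and drug for 1,440 women is already implied by the planned enrolment.
- *That a shortfall would be slow to repair*, because "Every dose will be produced during one series i.e. one batch". That describes how each dose is made, not how much is made or how long more would take.
- *That an added list would upset the balance of the arms.* Section 7.11.5 gives no block length, and both 1,200 and the missing 240 (40 × 6) divide by six. Complete blocks can be appended without harm.
- *That the 73% power quoted in Protocol 10.6.7 and SAP 6.8 confirms the figure here.* That sentence concerns drop-out at the interim look and its condition is incomplete; it is not about 1,200 women.

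**Conclusion.** The inconsistency is certain: 7.11.2 and 4.1 describe 1,200 women, and the rest of the protocol and the SAP describe 1,440. The gap is 240 randomisation numbers, 40 per arm. It is a consistency correction and not an error in the sample size calculation, which reproduces.

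The effect on power is conditional. It arises only if the 1-1200 range is treated as binding. With 30% also lost from analysis, power would be about 73.4% against 81.4% (stated as 80%), under the plan's assumptions of a one-sided 0.015 level, a 16.7-point margin, 50% responders and no true difference. With fewer women lost the reduction is smaller, and at 16% or less it disappears relative to the planned 168 evaluable per arm.

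The point is worth acting on because the range is an operative specification for the randomisation list and the labels.

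**What to change.** In Protocol 7.11.2, change the randomisation and label range to 1-1440, with the list generated in complete balanced six-arm blocks. Add a sentence saying that, if the interim drop-out rule raises the total above 1,440, the list will be extended in the same block structure. How the extension is arranged, whether as reserve numbers made at the start or complete blocks added later, is for the sponsor to choose. In Protocol 4.1, change 200 women per arm to 240.

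The cost is two wording changes, one added sentence and a longer randomisation list. No analysis, endpoint or sample size figure in 10.6.3 or in the SAP needs to change.

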7.11.3 Doses and treatment regimens

Participants will be randomised into:

- Tamoxifen 20 mg
- Tamoxifen 10 mg
- Tamoxifen 5 mg
- Tamoxifen 2.5 mg
- Tamoxifen 1 mg
- Placebo 0 mg

All treatments will be on a daily basis (1 tablet daily) for 6 months.

7.11.4 Investigational Medicinal Product accountability

The IMP will be dispensed to the study participant at baseline. The number of tablets given out will be recorded in both CRF and in the Product Accountability log in the Study file. We will ask the participant to bring back the container at next visit (after 6 months or by withdrawal/dropout) in order to count remaining tablets. Any unused tamoxifen (i.e. remaining tablets) should be saved for drug accountability and sent for destruction.

7.11.5 Method of assigning participants to treatment groups

Randomisation will be performed by a CMO (Galenica AB). The participants will be randomized in blocks in where the 6 arms are distributed evenly. The study participant emergency code envelopes are kept by a 24/7 service provider (Apoteket AB in Lund) during the whole study. Researchers do not have access to the randomisation list. This means that the study is triple blinded, i.e. neither study participant, Karma Study Centre, nor researchers know which medication product was used for each study participant.

7.11.6 Blinding

The study is double-blinded, placebo controlled randomised study and neither the investigators nor the participants will know who is on active treatment and at what doses (See 7.11.5 for method of assigning participants to treatment groups).

The randomization code (emergency envelopes) are held by Apoteket in Lund. The treatment code can only be broken if an investigator considers there is a valid medical or safety reason to break the blinding. The Investigator must have a reason to break the blinding, for example when the studied drug is likely to have a significant effect on the clinical management of the study participant. When the code is broken for an individual subject, a notification has to be given in the eCRF.

The study is also blinded for the person responsible for Mammographic Density assessments.

7.11.7 Prior and concomitant therapy

Other therapy that is considered necessary for the subject's welfare may be given at the discretion of the Investigator.

- Women using drugs that interfere with CYP2D6 expression such as Seroxat (paroxetine), Fontex (fluoxetin), Zyban / Voxra (bupropion) are not allowed during the study or used at study enrolment.
- Oestrogen and progesterone based hormone replacement therapy (oral), hormone contraceptive with hormones, e.g. hormonal contraceptive pills, or progesterone implants are not allowed during the study or used at study enrolment.
- Waran (warfarin) is not allowed during the study or used at study enrolment
- Non-medical approved drugs against hot-flushes including phytoestrogen are not allowed during the study or used at study enrolment.

All concomitant therapy must be recorded in the eCRF. No other drug under investigation may be used concomitantly with the study medication. Medication will be coded according to WHO's Anatomical Therapeutic Chemical (ATC) classification.

7.11.8 Treatment compliance

Compliance will be assessed throughout the study by i) calculating the number of tablets remaining at the final visit at the Karma Study Centre and comparing with the expected usage, ii) by web-questionnaires targeting adherence to therapy. The participant is defined as a complier if more than 80% of the tablets are taken.

8 SAFETY ASSESSMENTS

Safety assessment will consist of monitoring and recording Adverse Events (AE) and Serious Adverse Events (SAE). Women in fertile age will be asked to use high efficient birth control and pregnancy tests will be done if the women approve.

8.1 Participant Card

Participants will get a wallet sized Participant card containing essential information about the study and contact information to Karma Study Center (see appendix).

8.2 Birth control for women in fertile age

Premenopausal participants will be asked if they use any of the highly effective birth control methods mentioned below:

- 1. Hormonal contraception inhibiting ovulation.
 - a. Women on using exogenous female sex hormones will be excluded from the study since hormones affects mammographic density.
- 2. Intrauterine devices
 - a. Fully acceptable
- 3. Intrauterine hormone releasing systems
 - a. Fully acceptable since we do not believe that the low systemic hormone levels affects mammographic density. They do not influence the risk of breast cancer.
- 4. Bilateral tubal exclusion
 - a. Fully acceptable
- 5. Vasectomised partner
 - a. Fully accepted
- 6. Sexual abstinence
 - a. In most circumstances not an accepted method since the study continues for 6 months.

Methods #2-5 will be considered acceptable and in some few circumstances #6, depending on the wish of the participant.

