7.1.3 Baseline (Month 0)

Meeting with Investigator

- The investigator will explain the nature and aim of the study, its procedures, possible side effects, requirements and restrictions.
- The woman will sign the ICF before any further study related procedures are performed.
- A woman fulfilling the inclusion and exclusion criteria will be randomised to one of the six treatment arms; tamoxifen 20 mg, 10 mg, 5 mg, 2.5 mg, 1 mg or placebo. All treatments will be on a daily basis for 6 months
- The woman will receive a sufficient amount of IMP in order to take one tablet daily during 6 months
- Screening form, randomization number and other applicable information will be filled in by investigator in the eCRF.
- The participants will be asked if they allow to have two biopsies of the normal breast tissue taken at month 0 and 6. This is optional and complies with a separate study protocol (Protocol: Biopsy Karisma II)

Procedures at baseline

After meeting with investigator when ICF is signed and randomization is performed, the following will be obtained:

- In total 24 ml blood will be collected. The blood will be analysed for tamoxifen metabolites, plasma hormones, plasma proteins, metabolic markers. In addition, DNA will be extracted and plasma aliquots will be biobanked for later analyses.
- The participants will be asked to fill out two web-based questionnaires;
 - The Karma questionnaire including lifestyle factors that influence risk of breast cancer such as age at first birth, breast-feeding, etc., demographic, medical history, quality-of-life, and concomitant medication.
 - o Karisma II baseline questionnaire including general symptoms and tamoxifen related symptoms
- Pregnancy test (urine) will be offered women of childbearing age for safety
- Measurement of weight, length and waist
- Instructions are given on how to use and report events by the Karma-app
- Biopsy of the breast. This is optional and complies with an additional translational study protocol (Protocol: Biopsy Karisma II)

7.1.4 1 month after baseline (+2/-1 weeks)

• Karisma II follow up questionnaire including general symptoms, tamoxifen related symptoms, compliance and health care contact connected to possible side effects

- 7.1.5 3 months after baseline (+/- 2 weeks)
 - Karisma II follow up questionnaire including general symptoms, tamoxifen related symptoms, compliance and health care contact connected to possible side effects

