7.8 Inclusion criteria

To participate, the women must meet the following inclusion criteria:

- Attending the national mammography screening program, i.e. aged 40-74 and has performed a mammogram maximum 3 months prior to study inclusion
- Having a measurable mammographic density, i.e. ≥4.5 % density (volumetric) measured by Volpara
- Informed consent must be signed before any study specific assessments have been performed

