7.9 Exclusion criteria

To participate, the women must not meet any of the following exclusion criteria:

- Being pregnant or planning to become pregnant during the study period
- Any previous or current diagnosis of breast cancer (including carcinoma in situ)
- Mammographic BI-RADS code 3 or above at baseline mammography, or at a diagnostic mammography during time of treatment (the first 6 months of the study)
- Any previous diagnosis of cancer with the exception of non-melanoma skin cancer and in situ cancer of the cervix
- Currently using *oral* oestrogen and progesterone based hormone replacement therapy
- Current use of hormone contraceptive with hormones, e.g. hormonal contraceptive pills, or progesterone implants. Hormonal intrauterine devices are accepted.
- A history of thrombo-embolic disease such as embolies, deep vein thrombosis, stroke, TIA or cardiac arrest.
- Known APC (Activated protein C) resistance, an inherited hemostatic disorder
- A history of major surgery of the breast, e.g. reduction or enlargement, which might affect density measurements
- A history of immobilization, e.g. using wheelchair
- Known uncontrolled diabetes
- Hypertension at baseline, defined as systolic pressure higher than 140 mm Hg and diastolic higher than 90 mm Hg
- Use of drugs that interfere with CYP2D6 expression such as Seroxat (paroxetine), Fontex (fluoxetin) and Zyban / Voxra (bupropion)
- Use of Waran (warfarin)
- Non-medical approved drugs against hot-flashes including phytooestrogen
- Not able to understand study information and/or informed consent

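### No required step before randomisation verifies the pregnancy exclusion, and the contraception expected in section 8.2 is not an entry criterion

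*Protocol*

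**What the plan says.** **Pregnancy.** Protocol 7.9 excludes a woman for "Being pregnant or planning to become pregnant during the study period". Section 7.10 makes pregnancy a reason for withdrawal. Section 9.5.2 stops treatment at once if pregnancy occurs or is suspected.

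**Contraception.** Section 8 states: "Women in fertile age will be asked to use high efficient birth control and pregnancy tests will be done if the women approve". Section 8.2 opens with: "Premenopausal participants will be asked if they use any of the highly effective birth control methods mentioned below". It then comments on six methods. Ovulation-inhibiting hormones are ruled out because of their effect on density. Intrauterine devices, hormone-releasing intrauterine systems, tubal occlusion and a vasectomised partner are accepted. Abstinence is mostly not accepted. The section closes: "Methods #2-5 will be considered acceptable and in some few circumstances #6, depending on the wish of the participant".

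**Testing and order at month 0.** Under the investigator meeting, section 7.1.3 says: "A woman fulfilling the inclusion and exclusion criteria will be randomised to one of the six treatment arms". Under the same meeting the woman is given her full 6-month tablet supply. The next list begins: "After meeting with investigator when ICF is signed and randomization is performed, the following will be obtained". One item in it is: "Pregnancy test (urine) will be offered women of childbearing age for safety". The schedule of events (Appendix 14.3) shows the test once, at month 0, qualified as applying where applicable.

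**Consent.** Section 7.8 requires: "Informed consent must be signed before any study specific assessments have been performed".

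**The concern.** Two things in the text do not meet. First, the protocol has a pregnancy exclusion and a urine test, but the test comes after the decision that the exclusion governs, and the woman may decline it. Second, section 8.2 distinguishes accepted from unaccepted methods, which makes sense only if an accepted one is expected. No consequence follows when a woman reports using none.

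The main stake is participant safety. These are healthy women aged 40-74 for whom section 5.1 foresees no clear personal benefit, and five of the six arms receive tamoxifen. The protocol itself treats pregnancy on study drug as serious: immediate stop, follow-up of every pregnancy outcome, and miscarriages and birth defects handled as serious adverse events (9.5.2).

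There is also a smaller effect on the data. A positive test after allocation turns a woman who should never have been randomised into a withdrawal, and drop-out is the secondary endpoint (6.4).

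**Working it through.** No arithmetic beyond a count applies, so the relevant sections are set side by side.

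1. **Count of entry criteria.** Section 7.8 has 3: screening attendance at age 40-74 with a recent mammogram, density of at least 4.5%, and consent. Section 7.9 has 16. Total 3 + 16 = 19.
   - Requiring use of contraception: 0 of 19.
   - Requiring a negative pregnancy test: 0 of 19.
   - Excluding current or planned pregnancy: 1 of the 16 exclusions.

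2. **What was carried over from 8.2.** Section 7.9 takes over the bar on hormonal contraceptives and the allowance for hormonal intrauterine devices, and 7.11.7 extends the bar through the study. The expectation of an accepted method is not carried over. One class of effective contraception is thus removed without a replacement being required.

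3. **Order of steps.** Pre-screening (7.1.2) covers study information, density and blood pressure. At month 0, section 7.1.3 gives eligibility, randomisation and dispensing under the investigator meeting. The urine test stands in the following list, which by its own introduction comes after consent and randomisation. No sentence makes dispensing depend on the result.

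4. **Two women followed through the text.**
   - *Premenopausal, fertile, not pregnant, not planning pregnancy, using no method.* She is asked about contraception under 8.2 and answers none. No criterion in 7.8 or 7.9 is breached on that account, so 7.1.3 allows randomisation.
   - *Early pregnancy of which she is unaware.* She breaches 7.9, which is not limited to known pregnancy. Nobody is required to find this out. If she declines the test, it can go unnoticed. If she accepts and it is positive, she has already been allocated, so 7.10 and 9.5.2 apply and she is a post-randomisation withdrawal.

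5. **Later checks.** After month 0 the next scheduled visit is month 6; months 1 and 3 are web questionnaires. The schedule shows no repeat test. Sections 7.10 and 9.5.2 act only once pregnancy is known or suspected.

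6. **Number affected.** The documents give the age range but neither the premenopausal share nor contraceptive use, so no count can be derived.

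**The case against.** The best case for the plan is that it chose a voluntary approach and describes it consistently: women are asked about contraception, asked to use it, and offered a test. Section 8.2 nowhere says that a woman without an accepted method is ineligible. Two of its comments, on ovulation-inhibiting hormones and on hormone-releasing intrauterine systems, rest on density and not on protection from pregnancy. The one rule there that expressly excludes women does appear in 7.9. Pregnant women and those planning pregnancy are excluded, and suspicion alone stops treatment.

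Much of this stands. The contraception requirement is implied, not stated, and making the test a condition of entry is a deliberate change of design. What the objection does not explain is the comment on abstinence, which is mostly refused because the study lasts 6 months; that reads as a requirement. Nor does it give a reason for placing a safety test after the randomisation it should inform.

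A reader might infer three stronger points that the documents do not support:
- *That a woman with an undetected pregnancy meets all criteria.* She does not; she fails 7.9. The gap is in verification.
- *That tablets are taken before the test.* Test, randomisation and dispensing share one visit, so the test may well precede the first tablet.
- *That the qualifier in Appendix 14.3 is further evidence of a voluntary test.* In women aged 40-74 it more naturally limits the test to those who could be pregnant.

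**Conclusion.** The point holds as a gap in verification and in entry criteria. The plan as written can randomise a woman and dispense six months of study tablets without any required check of its own pregnancy exclusion. It can also enter a fertile premenopausal woman who uses no method that 8.2 accepts. The size is 0 of 19 entry criteria requiring contraception or a negative test, and one scheduled test, voluntary and listed after randomisation.

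It would go too far to say that the plan has no pregnancy safeguards, or that it breaks a contraception rule it has stated. The conclusion rests on reading the list in 7.1.3 as an order of events, which its introductory sentence supports, and on reading the grading in 8.2 as an expectation. The first part of the point, on testing, does not depend on the second reading. No power, margin or sample size figure changes. Any effect on the drop-out endpoint is probably small, so the case rests on safety.

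**What to change.** 1. **Section 7.1.3:** do the already planned urine test in women of childbearing potential directly after consent and before randomisation and dispensing, and require a negative result for entry. This keeps to the consent-first rule in 7.8.
2. **Section 8:** replace the clause that makes testing depend on the woman's approval, so that it agrees with 7.1.3. The qualifier in Appendix 14.3 can stay.
3. **Section 7.8:** add that women of childbearing potential use one of methods 2-5 of section 8.2 during the 6 months of treatment, or method 6 where the investigator documents acceptance. Define the group so that women who cannot conceive, for example after hysterectomy, are not caught by it.

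**Cost.** One inclusion criterion, one eligibility item in the eCRF, and one step moved within the month 0 visit; no new assay or visit. The downside is that women of childbearing potential who decline the test or use no accepted method become ineligible, in a number that the documents do not allow to be estimated.
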